Appendix A. Investigator Obligations	
Appendix B. Definity Product Insert	

SYNOPSIS

Protocol Title: 2D and 4D Contrast-enhanced Ultrasound Evaluation of Hepatocellular Carcinoma Chemoembolization

Trial Objectives: The primary objective of this trial is to:

- To evaluate the sensitivity and specificity of 2D and 4D contrast enhanced ultrasound for monitoring transarterial chemoembolization (TACE) response 1-2 weeks and 1 month post treatment as an alternative to contrast-enhanced magnetic resonance (MRI) or computed tomography (CT) imaging

The secondary aim of this trial is to:

- To develop quantitative biomarkers based on the ultrasound contrast agent kinetics for identifying patients requiring retreatment of residual disease.

Trial Design: This is an open-label, non-randomized trial that will be conducted at three clinical sites. The subject population will be patients undergoing transarterial chemoembolization for the treatment of hepatocellular carcinoma (HCC) at Thomas Jefferson University, The University of California, San Diego, and The Hospital of the University of Pennsylvania. Patients will receive a contrast-enhanced ultrasound (CEUS) exam the morning prior to embolization, approximately one week post-embolization, and at their one month MRI follow up (scheduled as part of their clinical standard of care).

Trial Population: This trial will consist of up to 210 adults (with a maximum of up to 100 at any institution) undergoing transarterial chemoembolization for the treatment of HCC split between Thomas Jefferson University, The University of California, San Diego, and The Hospital of the University of Pennsylvania.

Trial Procedures: Patients will be identified and consecutively approached from each institution's Hepatology / Transplant Surgery and Interventional Radiology practices (by each site's Hepatology or Interventional Radiology co-investigators). An investigator or research coordinator will explain the study to the patient. The patient will be given time to consider the risks and benefits of the study and to ask questions about participation. A consent form will be reviewed with the patient. A full history and physical

examination will be obtained from the patient's referring physician. If the subject is a woman of childbearing potential, she will have a urine pregnancy test prior to each CEUS study (the results of which will be made available to the subject prior to study initiation). In the event a patient presents with a lesion that is expected to be difficult to view on ultrasound (for example, smaller lesions located high on the liver dome), grayscale ultrasound imaging will quickly be performed to ensure the lesion is visible on ultrasound and that the patient is suitable for study inclusion.

Patients will undergo a total of three separate CEUS exams. These exams will consist of the baseline study prior to TACE therapy, a study 1-2 weeks post treatment that will coincide with clinical post-procedure follow-up by the interventional radiologist, and a study approximately one month post treatment when patients return for clinically scheduled CE-CT/MRI follow-up. If the patient fails to show up for the 1-2 week CEUS exam, they will not be excluded from the final ultrasound exam. Procedures and equipment for this trial will be used in accordance with standard clinical protocols and good clinical practices already in place at our hospitals.

The first three cases at each institution (baseline and at least one follow-up) will be performed under the guidance of at least one of the study PIs to ensure standardization amongst all three sites. The ultrasound examinations will be performed by a qualified sonographer. Efforts will be made to have all CEUS scans performed by the same dedicated sonographer, enabling us to evaluate operator dependence. During the ultrasound examination, the patient will be asked to lie in the supine position and a 20-22 gauge cannula will be placed in a superficial vein (preferably an antecubital vein). Ultrasound imaging will be performed using a state of the art Logiq E9 scanner with C1-5-D broad-spectrum convex transducer and a RAB2-5-D broad-spectrum real-time 4D transducer (GE Healthcare, Wauwatosa, WI). As part of this study, we have budgeted for the purchase of 3 4D probes (not routinely available in clinical practice) and the installation of GE's ultrasound volumetric and contrast imaging packages that provide 2D and 4D CEUS capabilities. In the event the patient has multiple lesions scheduled for treatment, up to 2 lesions will be imaged independently on CEUS. Patients will first undergo 2D baseline imaging. B-mode measurements and sweeps of the lesion in the transverse and sagittal planes will be performed, followed by standard power Doppler imaging (PDI). Following baseline imaging, patients will receive a bolus IV injection of up to 0.6 ml of Definity, followed by a 10 cc saline flush. Since Definity is currently only approved for echocardiography, we will apply to the FDA for an investigational new drug application for CEUS evaluation of TACE (similar to our previous study [Shaw et al. 2014]).

All CEUS imaging will be performed using the dual B-mode (used to locate anatomical features) and

nonlinear contrast (to identify the ultrasound contrast agent) imaging mode. A low mechanical index (< 0.1) will be used to minimize microbubble destruction during imaging. The standard nonlinear imaging frequency pairings in the contrast imaging software will be used (transmitting at 2 MHz, receiving at the 4 MHz harmonic), and gain settings will be adjusted to minimize nonlinear signals prior to contrast injection. Additionally, the focal zone will be placed at the approximate depth of the lesion to maximize the generation of nonlinear signals during CEUS. During the first contrast injection, 2D CEUS will be performed using the coded harmonics nonlinear imaging package on the unit. The approximate tumor mid-line will be imaged until homogenous liver enhancement is achieved (approximately 45 seconds post injection), followed by imaging sweeps through the tumor. Sweeps will then be acquired in the sagittal plane, before returning to the original plane. Imaging will be continued until contrast washout is observed (approximately 3-4 minutes), after which data will be digitally stored for later review. A ten to fifteen minute wait period will be observed between injections to allow for complete ultrasound contrast agent clearance. A region of interest encompassing the entire tumor volume and margin will then be selected in 4D mode. Baseline imaging of the tumor will be repeated in 4D mode in grayscale B-mode. A second bolus injection of up to 0.6 ml Definity followed by 10 cc saline flush will again be administered during continuous tumor imaging in 4D, which uses the machine's coded harmonics package. Data will be obtained until contrast washout is observed and then digitally stored in digital imaging and communications in medicine (DICOM) format for later review.

The proposed agent for the current study, Definity is a sterile non-pyrogenic suspension of liposome-encapsulated perfluoropropane microbubbles [Goldberg et al 2001; Miller & Nanda 2004]. The contrast agent is composed of a blend of three phospholipids contained in a matrix of sodium chloride, propylene glycol, and glycerin in water. The contrast agent is supplied in a vial that contains the phospholipids and perfluoropropane gas. The microbubble agent is supplied in a standard-size 2 ml vial and is prepared by shaking the vial with the aid of a shaking device (Vialmix: ESPE, Seefeld, Germany). Definity will be stored in a secure cabinet, with only the study investigators and research personnel having access. Definity is currently only approved for use in echocardiography. The agent will be used as an off-label indication for this study. We intend to apply for an FDA investigator-instantiated IND for the off-label usage of Definity for the evaluation of chemoembolization using drug eluting beads.

Statistical Methodology: Data analysis from this multi-center clinical trial will be performed to characterize 2D and 4D CEUS as a follow-up imaging tool for the evaluation of residual tumoral blood flow in patients with HCC treated with TACE. Our statistical analysis will address three major questions:

1. Does 2D and 4D CEUS 1-2 weeks post TACE yield sensitivity and specificity greater than 90% for identifying residual tumor blood flow, thereby providing reliable earlier identification (relative to the current clinical standard) of patients in need of retreatment?
2. Does 2D and 4D CEUS 1 month post TACE yield sensitivity and specificity greater than 90% for identifying residual tumor blood flow, thereby providing an accurate, safe, and cost-effective imaging alternative for identifying TACE patients in need of retreatment?
3. Are quantifiable biomarkers generated by parametric imaging of 2D and 4D CEUS exams able to differentiate between fully treated and incompletely treated masses by measuring blood flow kinetics?

The first three cases at each institution will be used as reader training cases and will not be included in the final analysis. In the event of all cases showing identical response (i.e. all incompletely or completely treated), the first case with an alternative outcome will be substituted for the 9th case. Following reader training, each reader (all of whom have previous experience with CEUS and volumetric ultrasound) will be asked to evaluate all 201 remaining cases. 2D and 4D CEUS exams will be read separately and only after randomization. Readers will first be asked to review both the patient's baseline CE-MRI/CT and CEUS exams to identify the size and location of the treated mass. Following baseline review, each reader will review the 1-2 week and 1 month CEUS exam (in random order). Intratumoral blood flow will be assessed as present or not present. Readers will then be asked to interpret the patient's 1 month follow-up CE-MRI/CT images and again evaluate the need to retreat based on residual blood flow. Finally, when available, readers will review subsequent CE-MRI/CT imaging studies (up to six months post TACE). MRI/CT evaluations will be based on mRECIST criteria. All imaging studies will be read twice by each reader. Studies will be presented in random order. The second round reads will be performed at least one month after the first. Outcomes will be defined as incompletely treated (i.e. requiring retreatment) based on (in order of preference of reference standard): a) pathological examination of explanted livers demonstrating live tumors; b) tumor enhancement seen with CT or MR and confirmed via angiography during retreatment; c) tumor growth on 6 month follow-up CE-CT/MRI; or d) asymmetrical or nodular tumor enhancement on CE-MRI/CT on 6 month follow-up. Incomplete treatment on CEUS (2D or 4D) will be evaluated by each reader and evidenced by the tumor showing either residual blood flow after treatment or nodular peripheral blood flow.

For statistical questions 1-2, sensitivity (the ability to detect patients in need of retreatment) and specificity (the ability to identify patients who do not require retreatment) will first be calculated on a reader by reader basis. Four 2 x 2 tables will be constructed comparing the need for re-treatment based on the clinical gold standard and CEUS, tabulating true positives, false positives, false negatives, and true negatives for CEUS

at 1-2 weeks and 1 month for both 2D and 4D CEUS and used to calculate sensitivity, specificity, accuracy, positive predictive value, and negative predictive value. Statistical significance between the reference standard and each of the 4 CEUS groups will be determined using a McNemar test. These values will also be calculated based on the majority decision (i.e. 4 or more readers in agreement). In the event of discordant readings during this analysis, tumor outcome will be decided by consensus by the two readers at TJU. Differences between techniques (2D vs. 4D) and time points (1-2 weeks vs. 1 month post treatment) will be determined by comparing areas under the receiver operating characteristic curves for each modality/time point based on necessity of tumor retreatment. Intra-rater and inter-rater variability will be calculated using a Shrout and Fleiss Interclass Correlation [Shrout and Fleiss 1979]. Finally, a logistical regression and analysis of variance will be performed to determine if significant variations exist between individual sites (to determine operator dependence), lesion size (tumor size dependency) or between patients treated with cTACE vs. DEB-TACE (treatment dependency).

For statistical question 3, all quantitative parameters will be compared between fully treated and incompletely treated masses using a Student's t-test. Additionally, lesions that demonstrate lack of residual enhancement at 1 month, but show recurrence at 6 month follow-up, will be compared to completely treated masses to determine if quantitative CEUS parameters can detect this lower level of residual disease. Statistical analysis will be performed with assistance from the biostatistician co-investigator using Stata 12.0 (Stata Corp, College Station, TX) with p values < 0.05 considered statistically significant after a Bonferroni-type adjustment for multiple tests. These statistical tests will answer our three major questions regarding the sensitivity and specificity of 2D and 4D CEUS as an imaging tool for the follow-up of TACE at 1-2 weeks and 1 month, as well as the influence of operator, reader, tumor size, and embolization material.

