3.1 Trial Duration

Individual participation in this trial will be limited to three ultrasound imaging studies. Exams will take place the morning prior to treatment, one to two weeks post embolization, and prior to the patient's one month follow-up (scheduled as part of clinical care). If the patient fails to show up for the one week, CEUS exam, they will not be excluded from the final ultrasound exam. The entire ultrasound imaging protocol will require approximately one hour including a 30 min observation period. Patients will be monitored for at least 30 minutes before being escorted to procedure or clinically scheduled imaging.

Subject recruitment is expected to last 5 years (January 2016 – December 2020). Analysis and publication of results are expected to take an additional 2 months (December 2020– January 2021). Volunteer Registry Database forms will be submitted to the National Institute of Health's Office of Regulatory Compliance and Quality at the completion of the research study.

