5.1 Administration

All contrast injections will be supervised by a board certified physician. Resuscitation equipment and trained personnel will be immediate proximity to the patient during each contrast-enhanced ultrasound exam. Definity will be administered by bolus IV injection through an 18- to 20-gauge angiocatheter placed in a peripheral arm vein, preferably an antecubital vein. Subjects will be instructed not to move their arm during the administration of the contrast agent. Subjects will receive a bolus injection of up to 0.6 ml. All injections will be performed at a steady rate not to exceed 1 ml/sec. If contrast is not detected within the tumor, the injection may be repeated with the total cumulative dose not to exceed 1.5 ml. Each bolus injection of Definity will be followed with a very slow flush of 10 ml of normal saline.

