5.4 Blinding and Unblinding Methods

This is an open-label trial; therefore, no blinding or unblinding procedures for the trial drug are required.

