6. TRIAL PROCEDURES

6.1 Patient Enrollment

Patients will be identified and consecutively approached from each institution's Hepatology / Transplant Surgery and Interventional Radiology practices (by each site's Hepatology or Interventional Radiology co-investigators). An investigator or research coordinator will explain the study to the patient. The patient will be given time to consider the risks and benefits of the study and to ask questions about participation. A consent form will be reviewed with the patient

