frequency pairings in the contrast imaging software will be used (transmitting at 2 MHz, receiving at the 4 MHz harmonic), and gain settings will be adjusted to minimize nonlinear signals prior to contrast injection. Additionally, the focal zone will be placed at the approximate depth of the lesion to maximize the generation of nonlinear signals during CEUS. During the first contrast injection, 2D CEUS will be performed using the coded harmonics nonlinear imaging package on the unit. The approximate tumor mid-line will be imaged until homogenous liver enhancement is achieved (approximately 45 seconds post injection), followed by imaging sweeps through the tumor. Sweeps will then be acquired in the sagittal plane, before returning to the original plane. Imaging will be continued until contrast washout is observed (approximately 3-4 minutes), after which data will be digitally stored for later review. A ten to fifteen minute wait period will be observed between injections to allow for complete ultrasound contrast agent clearance. A region of interest encompassing the entire tumor volume and margin will then be selected in 4D mode. Baseline imaging of the tumor will be repeated in 4D mode in grayscale B-mode. The line density (a measure of image quality) may also be adjusted to achieve adequate volume acquisition rates (>0.5 volumes/ second). A second bolus injection of up to 0.6 ml Definity followed by 10 cc saline flush will again be administered during continuous tumor imaging in 4D, which uses the machine's coded harmonics package. If sufficient contrast is not detected in either mode, the injection may be repeated with the total cumulative study dose not to exceed 1.5 ml. Data will be obtained until contrast washout is observed and then digitally stored in digital imaging and communications in medicine (DICOM) format for later review.

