reader. Studies will be presented in random order. The second round reads will be performed at least one month after the first. Outcomes will be defined as incompletely treated (i.e. requiring retreatment) based on (in order of preference of reference standard): a) pathological examination of explanted livers demonstrating live tumors; b) tumor enhancement seen with CT or MR and confirmed via angiography during retreatment; c) tumor growth on 6 month follow-up CE-CT/MRI; or d) asymmetrical or nodular tumor enhancement on CE-MRI/CT on 6 month follow-up. Incomplete treatment on CEUS (2D or 4D) will be evaluated by each reader and evidenced by the tumor showing either residual blood flow after treatment or nodular peripheral blood flow.

For questions 1-2, sensitivity (the ability to detect patients in need of retreatment) and specificity (the ability to identify patients who do not require retreatment) will first be calculated on a reader by reader basis. Four 2 x 2 tables will be constructed comparing the need for re-treatment based on the clinical gold standard described above and CEUS, tabulating true positives, false positives, false negatives, and true negatives. A table will be created for CEUS at 1-2 weeks and 1 month for both 2D and 4D CEUS and used to calculate sensitivity, specificity, accuracy, positive predictive value, and negative predictive value. Statistical significance between the reference standard and each of the 4 CEUS groups will be determined using a McNemar test. These values will also be calculated based on the majority decision (i.e. 4 or more readers in agreement). In the event of discordant readings during this analysis, tumor outcome will be decided by consensus by the two readers at TJU. Differences between techniques (2D vs. 4D) and time points (1-2 weeks vs. 1 month post treatment) will be determined by comparing areas under the receiver operating characteristic curves for each modality/time point based on necessity of tumor retreatment. Intra-rater and inter-rater variability will be calculated using a Shrout and Fleiss Interclass Correlation [Shrout and Fleiss 1979]. Finally, a logistical regression and analysis of variance will be performed to determine if significant variations exist between individual sites (to determine operator dependence), lesion size (tumor size dependency) or between patients treated with cTACE vs. DEB-TACE (treatment dependency).

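### Nothing in the available text keeps follow-up CEUS findings from the treating interventional team, whose retreatment and angiogram can set the reference label; specificity is mainly exposed

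*Combined protocol and SAP*

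**What the plan says.** The early follow-up exam is "a study 1-2 weeks post treatment that will coincide with clinical post-procedure follow-up by the interventional radiologist" (Synopsis, Trial Procedures). Section 3.1 places the last exam "prior to the patient's one month follow-up (scheduled as part of clinical care". Patients are identified and approached "by each site's Hepatology or Interventional Radiology co-investigators" (6.1), so the treating specialty belongs to the study team. On who is present, section 5.1 says only: "All contrast injections will be supervised by a board certified physician". Independence from the treating team is not required.

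The whole of section 5.4 reads: "This is an open-label trial; therefore, no blinding or unblinding procedures for the trial drug are required". On the images, section 6.3 says that they are "then digitally stored in digital imaging and communications in medicine (DICOM) format for later review". Section 7.1.1 adds that image data are de-identified and moved to a secure server at the lead site.

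Section 7.2 ranks four ways for a lesion to be called incompletely treated. The first is "a) pathological examination of explanted livers demonstrating live tumors". The second is "b) tumor enhancement seen with CT or MR and confirmed via angiography during retreatment". Criteria c and d are growth, or asymmetrical or nodular enhancement, on six-month CE-CT/MRI.

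**The concern.** Criterion b comes into being only when the clinical team retreats, and it is met only when the angiogram is judged to confirm the enhancement. If the people making those two judgments have seen flow on CEUS, an equivocal MRI may be resolved towards retreatment and a faint angiographic finding towards confirmation. A lesion that would have counted as a CEUS false positive then becomes a true positive. The reference has partly followed the test it is meant to judge.

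The plan gives clinicians some reason to lean on CEUS. Section 1.1 says that pilot work suggests it may be more accurate than CE-MRI/CT at one month, and that retreatment earlier than the usual interval is feasible. Once a lesion has been retreated, six-month imaging shows the retreated lesion and no longer checks the first label cleanly.

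This is separate from the order in which study readers view images. Blinding the readers would not protect a label formed in the clinic. Nor can analysts repair it afterwards if nobody recorded which labels were made with CEUS known.

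**Working it through.** **1. The plan's own figures.** Section 7.2.1 tests 90% against 98% at alpha 0.05 with prevalence 66.7%. An exact one-sided binomial test reproduces the last row of its table:
- Sensitivity, 133 positives: reject at 126 or more; attained alpha 0.0385, power 0.9945.
- Specificity, 67 negatives: reject at 65 or more; attained alpha 0.0307, power 0.8494.

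The stated 99% and 85% are therefore correct on their own terms, which include a reference that does not depend on CEUS.

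**2. Starting table under the null.** The text gives both 135 and 133 positives. Since 201 × 0.667 = 134.1, I use 134 positive and 67 negative. With true sensitivity and specificity of 90%: TP = 120.6, FN = 13.4, TN = 60.3, FP = 6.7.

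**3. Relabelling through criterion b.** Assumption, not in the documents: a share s of CEUS false positives becomes reference-positive.
- Apparent specificity = 60.3 / (60.3 + (1 − s) × 6.7)
- Apparent sensitivity = (120.6 + s × 6.7) / (134 + s × 6.7)

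**4. Chance of false success on specificity.** For 61 to 67 negatives, the exact one-sided 0.05 test allows at most two false positives. If each of 67 truly negative lesions is a CEUS false positive with probability 0.10 and then escapes relabelling with probability 1 − s, the number of false positives left is binomial(67, 0.10 × (1 − s)). False success is the probability that this number is 2 or fewer. At s = 0.2:
- 0.92^67 = 0.0037
- 67 × 0.08 × 0.92^66 = 0.0218
- 2211 × 0.08² × 0.92^65 = 0.0627
- Sum = 0.088

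| s | lesions relabelled (s × 6.7) | apparent specificity | false success | apparent sensitivity |
|---|---|---|---|---|
| 0 | 0 | 90.0% | 3.1% | 90.0% |
| 10% | 0.7 | 60.3/66.33 = 90.9% | 5.3% | 121.27/134.67 = 90.0% |
| 20% | 1.3 | 60.3/65.66 = 91.8% | 8.8% | 121.94/135.34 = 90.1% |
| 30% | 2.0 | 60.3/64.99 = 92.8% | 14.4% | 122.61/136.01 = 90.1% |

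**5. With a stricter alpha.** Section 7.2 calls for a Bonferroni-type adjustment without giving the number of tests. If it covered the four CEUS groups (assumption: 0.05/4 = 0.0125), only one false positive would be allowed. The first two terms of the same sum give 0.7%, 1.4%, 2.6% and 4.7% for s = 0, 10%, 20% and 30%. The absolute rates fall below 5%, but the growth relative to no relabelling remains.

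**6. Why dropping criterion-b labels would not reveal the problem.** Specificity is TN/(TN + FP). Every criterion-b lesion is reference-positive and enters only TP or FN, so removing those lesions leaves TN, FP and specificity unchanged.

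**The case against.** The strongest reply is that the route is inferred. No text reports CEUS to clinicians or lets it guide retreatment. A sonographer scans, the formal reads are done later off-line, the data go de-identified to a server, and the background places the retreatment decision on MRI/CT. The shared visit may be only scheduling, and the enrolment text does not say that the interventional co-investigators attend the exam, decide on retreatment or read the angiogram. Part of the personnel section (Appendix A, F) was not available for this review and may bear on this. All of that stands. A reader might infer that CEUS results are passed on and that the labels are biased; the documents do not show either. But storage for later review and de-identified transfer do not restrict who sees flow at the scanner or opens the stored images.

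A reader might also infer that sensitivity and specificity are inflated alike. The documents do not support that. Criterion b creates only positive labels, and it also needs CT or MR enhancement, so CEUS alone cannot produce one. A lesion watched after a clean CEUS can still be called positive at six months under c or d. Explant pathology is the criterion least open to influence.

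Finally, the figures are an illustration. The documents give no split of labels by criterion and no share of lesions open to influence. The one-sample exact test appears only in the sample-size section; section 7.2 itself names McNemar tests.

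**Conclusion.** The point holds as a missing safeguard. The timing of both follow-up exams, the place of the interventional team in the study and a reference criterion that depends on that team's actions leave a route from test to reference that no available text closes. It mainly threatens specificity, which is also the endpoint with less power. Under the assumptions shown, about two relabelled lesions among 201 would raise the chance of a false claim of specificity above 90% from 3.1% to 14.4% in the unadjusted one-sided test. The true share could be zero, and an adjusted alpha gives lower rates. The plan's power figures are not in error.

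**What to change.** 1. In sections 5.4 and 6.3, state that follow-up CEUS images and impressions are research data. They stay out of the clinical record and are not given to the clinicians whose decision or angiogram reading sets the reference. This lasts until the lesion's one-month CE-MRI/CT decision and, if it is retreated, its angiographic finding are recorded. Ending it at the one-month decision would leave the angiogram exposed. The sponsor defines the safety exceptions.
2. For every lesion, record which criterion (a to d) set the label, or for a reference-negative lesion the examination on which that rested, and whether any CEUS result was known at the time.
3. As a sensitivity analysis, repeat the tables for questions 1 and 2 without any lesion, reference-positive or reference-negative, labelled with CEUS known, and report results by criterion. Do not drop criterion-b labels alone.

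Cost: protocol wording, one or two case-form items and one extra table. The research exam does not inform care before the reference is recorded. The sensitivity table will rest on fewer lesions, possibly a selected group. Where the treating physician attends the exam, the item is marked as known and no extra staff are needed.
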